7.6.4 Sensitivity Analyses for the Primary Efficacy Endpoint

7.6.4.1 Using PP Population

Primary efficacy analysis will be conducted on the PP population as a supportive analysis.

7.6.4.2 Using ANCOVA

The analysis of covariance (ANCOVA) will be conducted for the two primary tests (Dysport 600 U vs. placebo, and Dysport 800 U vs. placebo), with the change of the weekly number of UI episodes from study baseline as response variable, including treatment group, stratification variables [the aetiology of NDO (SCI or MS) and prior intradetrusor BTX-A usage for UI (BTX-naïve or BTX-non-naïve)] and study baseline value of weekly number of UI episodes as covariates.

The least square means (LSMEANS) of the change of weekly number of UI at Week 6 in each group with standard error, the difference of mean between the treatment groups, the 95% CI of the difference and the p-value for treatment group will be presented.

The SAS codes of ANCOVA for reference are below.

```
CCI  
[Redacted SAS code for ANCOVA]
```

CCI [redacted]
[redacted]
[redacted]
[redacted]
[redacted]
[redacted]
[redacted]
[redacted]

7.6.4.3 Using MI

In presence of missing data in the primary efficacy endpoint, a multiple imputation approach for handling missing data will be undertaken on the mITT population. CCI [redacted]

[redacted]
CCI [redacted]
[redacted]
[redacted]

CCI [redacted]
[redacted]
[redacted]
[redacted]
[redacted]

[redacted]
[redacted]
[redacted]
[redacted]
[redacted]
[redacted]
[redacted]
[redacted]
[redacted]
[redacted]

[redacted]
[redacted]
[redacted]
[redacted]
CCI [redacted]
[redacted]
[redacted]

In above codes, the variables are defined as:

CCI [redacted]
[redacted]

7.6.4.4 Using Mis-Stratification Factors

As discussed in Section 5.6.2, the primary endpoint will be analysed with the MMRM using the incorrect stratification factors as recorded in IVRS for the mITT population.

7.6.5 Hierarchical Analysis of Secondary Efficacy Endpoints

As specified in Section 7.6.12, a hierarchical analysis will be performed in the order listed for the following six secondary efficacy endpoints at Week 6 after the first IMP administration:

- 1) Mean change from study Baseline in the MCC
- 2) Mean change from study Baseline in the MDP during storage
- 3) Mean change from study Baseline in the Vol@1stIDC
- 4) Proportion of subjects with no episodes of UI (i.e. continence is achieved)
- 5) Proportion of subjects with no IDCs during storage
- 6) Mean change from study Baseline in the I-QoL total summary score

The Derivation rules are specified in Section 3.2 and Appendix II.

For 1), 2) and 3), an ANCOVA model will be fitted using the “mean change” endpoint, as the response variable to obtain the p-value of treatment groups. The model will be the same as the sensitivity analyses for the primary efficacy endpoint in 7.6.4.2. The LSMEANS of the mean change from study baseline at Week 6 in each group with standard error, the difference of mean between the two treatment groups, the 95% CI of the difference and the p-value for treatment group will be presented.

For 4), a logistic generalised linear mixed model (GLMM) for repeated measures will be fitted for UI responses using repeated measurements at Week 2, Week 6, and Week 12. The “proportion of subjects with no episodes of UI” will be analysed as a response variable, the model will include treatment group, stratification variables, study baseline value, visit (week 2, week 6 and week 12), study baseline*visit and treatment*visit interactions as fixed effect. The study baseline value will be weekly number of UI episodes. The logistic GLMM is fitted using the logit link and the binomial distribution. Odds ratios, 95% CIs of odds ratio, and p-values for treatment group comparisons at each visit (week 2, week 6 and week 12) will be presented.

The SAS codes of GLMM for reference are below.

```
CCI
[Redacted SAS code]
```

CCI
[Redacted]
[Redacted]
[Redacted]

For 5), a logistic regression model will be performed with “proportion of subjects” as the response variable. The model will include treatment group, and stratification variables.

Odds ratio, 95% CI of odds ratio, and p-value will be presented.

The SAS codes of logistic regression for reference are below.

CCI
[Redacted]
[Redacted]
[Redacted]
[Redacted]
[Redacted]
[Redacted]
[Redacted]
[Redacted]

For 6), MMRM model will be fitted using the “mean change” endpoint, as the response variable to obtain the p-value of treatment groups. The model will be the same as primary analysis model in section 7.6.3. The least square means of change at Week 6 in each group with standard error, the mean difference of pairwise comparison, the 95% CI of the difference and the p-value for the treatment groups will be presented for each model.

If the testing procedure is stopped at the end of any particular step, the outcomes of the following steps will be presented and used for description only and no formal statistical conclusion will be drawn.

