7.6.3 Primary Efficacy Analysis

The primary efficacy endpoint is mean change in the weekly number of UI episodes from study baseline to Week 6 after the first treatment. Seven-day bladder diaries that contain data recorded on at least 5 days will be included in the analysis.

As all subjects should have visits up to and including week 12, but thereafter visits are dependent on whether the subject receives retreatment, statistical testing between treatment groups will be performed only up to Week 12, inclusive. Descriptive statistics table will present any timepoint.

Weekly number of UI episodes and the mean change from study baseline will be presented for the DBPC Cycle. The mixed model repeated measures (MMRM) analysis will be conducted with the change of the weekly number of UI episodes from study baseline as response variable. Fixed effect variables include treatment group, visit (Week 2, Week 6 and Week 12), treatment-by-visit interaction, stratification variables [the aetiology of NDO and prior intradetrusor BTX-A usage for UI] and study baseline value of weekly number of UI episodes. Random effect will include the subject effect. An unstructured covariance matrix will be specified in the mixed

model to account for within subject correlation. If model fails to converge, the structure of first order autoregressive AR (1), compound symmetry (CS) or variance components (VC) will be used.

The least square means (LSMEANS) of the change of weekly number of UI at each visit in each group with standard error, the difference of mean between the two treatment groups at each visit, the 95% CI of the difference and the p-value for treatment group will be presented. The comparison of main interest will be treatment difference at Week 6.

The SAS codes of MMRM for reference are below.

```
CCI  
[Redacted SAS code for MMRM]
```

The validity of the model assumptions of normality will be investigated using residual plots. The LS means of change from study baseline for weekly UI in the DBPC and Dysport Cycles will be presented in line plots by treatment groups.

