7.6.6.2 Urodynamic Filling Cystometry Parameters

See Section 3.2 for list of urodynamic endpoints. The summary tables for mean values at Week 6 and the mean change from study baseline will be presented using descriptive statistics for continuous endpoint. Number and percentage of subjects with no IDC will be also summarised.

For DBPC treatment cycle, MMRM model will be used for continuous endpoints, as described in section 7.6.3. A logistic regression will be used to analyse proportion of subject with no IDC.

Statistical Analysis Plan

Version: Final v2.0

Date of Issue: 21-

September-2018

Ipsen Protocol No. D-FR-52120-222

Covance Study ID:

000000146259

Bar charts of the LS means of changes will be plotted for MCC, MDP, Vol@1stIDC. In addition, a bar chart for the proportion of subjects with no IDC at Week 6 will be plotted.

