For the DBPC Cycle for I-QOL and EQ-5D-5L, mean change from study baseline to Week 6 and Week 12, will be analysed using MMRM, similar to the primary efficacy analysis. Mean mPGI-I score at Week 2, Week 6, Week 12 will be analysed as a response variable, using MMRM as in the supportive primary analysis, without baseline factor for mPGI-I.

The LS means of change from study baseline in DBPC cycle for I-QoL total summary score at all timepoints will be presented in a line plot by treatment groups up to Week 12.

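### As written, the models for MCC, MDP, Vol@1stIDC and I-QoL carry over baseline weekly UI as their only baseline covariate; the SAP should name each endpoint's own baseline

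*SAP*

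**What the plan says.** For hierarchical endpoints 1 to 3, SAP 7.6.5 states that "an ANCOVA model will be fitted using the “mean change” endpoint, as the response variable to obtain the p-value of treatment groups" and then "The model will be the same as the sensitivity analyses for the primary efficacy endpoint in 7.6.4.2". Section 7.6.4.2 lists treatment group, the two stratification variables and "study baseline value of weekly number of UI episodes as covariates". No other baseline value is named.

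For endpoint 6 (I-QoL total score), 7.6.5 says "The model will be the same as primary analysis model in section 7.6.3". The fixed effects in 7.6.3 again include the "study baseline value of weekly number of UI episodes".

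For endpoint 4 (continence), 7.6.5 does name the baseline: "The study baseline value will be weekly number of UI episodes". The endpoint 5 model (no IDCs) has treatment and stratification variables only.

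Two further statements bear on the question. SAP 7.6.6.3 models mPGI-I "using MMRM as in the supportive primary analysis, without baseline factor for mPGI-I". SAP 7.6.6.2 says of the urodynamic measures that an "MMRM model will be used for continuous endpoints, as described in section 7.6.3", which differs from the ANCOVA in 7.6.5.

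The SAS code under 7.6.3 and 7.6.4.2 is redacted, and Appendix II is not in the public text.

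**The concern.** In 7.6.4.2 the response is change in weekly UI, so baseline weekly UI is the response's own baseline. Section 7.6.5 replaces the response with change in MCC, MDP or Vol@1stIDC and says nothing about replacing the covariate. A programmer who follows the sentence exactly would adjust a change in bladder capacity or detrusor pressure for a count of incontinence episodes. The I-QoL model has the same gap.

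Adjusting a change score for its own baseline normally removes variance and corrects for chance imbalance in that baseline. MCC is the first secondary step under SAP 7.6.2. If it is not significant, the procedure stops and the remaining five endpoints are descriptive. A covariate that can be read in two ways therefore allows two different p-values at the step on which the rest of the hierarchy depends.

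**Working it through.** **The plan's own figure.** The documents give a power calculation only for the primary endpoint: difference 21 − 12 = 9 episodes, SD 20, two-sided alpha 0.025, power 80%, 96 per group (Protocol 9.2, SAP 2.3). The normal approximation gives 2 × 20² × (2.241 + 0.842)² / 9² ≈ 94. The noncentral t gives 96 (power 79.9% at 95, 80.4% at 96). The stated figure reproduces. It concerns weekly UI, which is adjusted for its own baseline, so this point does not touch it.

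**Which endpoints are affected.**

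| Hierarchical endpoint | Model defined by | Baseline covariate carried over |
|---|---|---|
| 1 MCC, 2 MDP, 3 Vol@1stIDC | 7.6.4.2 (ANCOVA) | weekly UI |
| 4 Continence | written out in 7.6.5 | weekly UI, stated |
| 5 No IDCs | written out in 7.6.5 | none |
| 6 I-QoL total score | 7.6.3 (MMRM) | weekly UI |

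Endpoints 1, 2, 3 and 6 are affected.

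**Size of the possible precision loss.** The documents give no SD, effect, power or baseline-to-Week 6 correlation (rho) for these endpoints, so the inputs are assumptions: equal variance s² at baseline and Week 6, a UI baseline unrelated to the urodynamic change, and 80% power under own-baseline adjustment at two-sided 0.05.

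- Change score without own baseline: variance 2s²(1 − rho).
- Own-baseline ANCOVA: residual variance s²(1 − rho²).
- Ratio of the second to the first: (1 + rho)/2.
- Power of the literal model: Φ[(1.960 + 0.842) × √((1 + rho)/2) − 1.960].

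| rho | Ratio | Power from 80% | Power from 90% | Power from 80%, alpha 0.025 | N multiple to recover |
|---|---|---|---|---|---|
| 0.3 | 0.65 | 61.7% | 74.3% | 59.6% | 1.54 |
| 0.5 | 0.75 | 67.9% | 80.2% | 66.6% | 1.33 |
| 0.7 | 0.85 | 73.3% | 84.8% | 72.6% | 1.18 |
| 0.9 | 0.95 | 78.0% | 88.5% | 77.7% | 1.05 |

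A simulation at rho 0.5 with 99 per arm (110 × 0.90) and 40,000 runs gave power of 67.1% with the UI baseline and 79.0% with the own baseline. Type I error was 0.051 and 0.049, so both models hold their level.

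**Sensitivity to equal variances.** In general the extra variance of the unadjusted change score is (SD₀ − rho × SD₆)², where SD₀ and SD₆ are the baseline and Week 6 SDs. With rho 0.5 and SD₀ = 1:

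- SD₆ = 1.5: the ratio is 1.6875/1.75 = 0.964 and power is about 79%.
- SD₆ = 0.8: the ratio is 0.48/0.84 = 0.571 and power is about 56%.

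The extra variance is never negative, so in large samples own-baseline adjustment is never the less precise choice.

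**The case against.** The strongest objection is that the sponsor may already mean own-baseline adjustment. In 7.6.4.2 the covariate is the response's own baseline, so calling the model the same can mean the same structure with the baseline following the response. Three things support this:

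- mPGI-I, which has no baseline, is modelled without a baseline factor. That exception would be unnecessary if baseline UI were simply carried over.
- The endpoint 5 model has no UI baseline. Its own baseline would be nearly constant, because sites confirm IDCs at Screening.
- Other cross-references cannot be literal. The model in 7.6.3 uses Weeks 2, 6 and 12, yet I-QoL is not collected at Week 2 and urodynamics are repeated only at Week 6.

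This stands, and it rules out some stronger readings. A reader might infer that these endpoints certainly will not be adjusted for their own baseline. The text is ambiguous, and the redacted code might settle it. A reader might also take the explicit baseline for endpoint 4 as proof that no own-baseline convention exists. It is not proof: entry requires at least two UI episodes a day, so baseline continence is constant and the SAP had to name some other baseline measure.

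The objection does not remove the gap. The prose names one covariate and replaces it nowhere, and unreliable cross-references are a reason to state the covariate.

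**Conclusion.** This is a clarification worth making at no cost, not an error that threatens the trial's validity. As written, four hierarchical endpoints carry the UI baseline and no text names their own. If the literal model is run, type I error and the primary analysis are unaffected, but precision can be lost.

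From an assumed 80%, power falls by about 18 points at rho 0.3, 12 at 0.5, 7 at 0.7 and 2 at 0.9. These figures rest on equal variances, an uninformative UI baseline and the assumed 80% starting point.

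A reader might infer that the MCC test is underpowered or likely to fail. The documents do not support that. They give no effect or SD for MCC, and with a large enough effect the loss would not matter.

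**What to change.** In SAP 7.6.5, state that for endpoints 1, 2, 3 and 6 the baseline covariate is the study baseline value of that same endpoint (MCC, MDP, Vol@1stIDC, I-QoL total score) and that it replaces baseline weekly UI episodes.

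Make the same change for the continuous endpoints in 7.6.6.1.2, in 7.6.6.2, and for I-QoL and EQ-5D-5L in 7.6.6.3. Leave mPGI-I without a baseline term. While editing 7.6.6.1.2, correct its pointer: it describes an MMRM but refers to 7.6.4.2, which is the ANCOVA.

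Reconcile the ANCOVA in 7.6.5 with the MMRM in 7.6.6.2, so that each urodynamic endpoint has one stated model. With a single post-treatment assessment at Week 6, visit terms and a within-subject covariance have nothing to estimate.

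The cost is a few sentences and one covariate per model, made before database lock as SAP section 1 requires of amendments. The baselines are already collected. No subject is lost by adding the covariate, because a change score cannot be computed without that baseline. If own-baseline adjustment is already intended, only the text changes.

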7.3.2 Urodynamic Examination

All subjects will have a standardised urodynamic (filling cystometry) assessment at Screening and again at Week 6 following the first IMP administration.

Urodynamics will be conducted according to International Continence Society recommendations [20]. Full details of the urodynamic procedures including standardisation, training, equipment setup, subject preparation, trace annotations, calculations and central review process are contained in a separate Study Specific Urodynamic Manual.

All urodynamic procedures will be covered with a minimum of 2 days of appropriate prophylactic antibiotics. See Section 6.4.1.2 for further details on antibiotic prophylaxis in the study.

All urodynamic data will be reviewed by independent central reviewers to determine the final values for the urodynamic parameters. The central reader's determination will be used for analysis purposes.

During Screening the site will determine if the subject has NDO via the presence of IDCs (inclusion criterion #15); without confirmation from the central reader.

The following urodynamic parameters will be obtained (Table 20):

Table 20 Urodynamic Parameters

Parameter	Unit	Calculation
MCC	mL	Total instilled volume or instilled volume just prior to the terminal IDC minus incontinent volume
MDP	cm H ₂ O	Peak detrusor pressure during storage (filling) phase minus trace baseline pressure
Presence of IDC(s)	N/A	N/A
Vol@1 st IDC	mL	Instilled volume when first IDC commences
PdetMax@1 st IDC	cm H ₂ O	Peak detrusor pressure during first IDC minus trace baseline pressure
EFP	cm H ₂ O	Detrusor pressure at end of filling or just prior to the terminal IDC minus trace baseline pressure
DC	mL/cm H ₂ O	Change in bladder volume divided by change in detrusor pressure (usually measured as MCC divided by EFP)

DC=detrusor compliance; EFP=end fill pressure; IDC=involuntary detrusor contraction; MCC=maximum cystometric capacity; MDP=maximum detrusor pressure; PdetMax@1stIDC=maximum detrusor pressure at first involuntary detrusor contraction; Vol@1stIDC=volume at first involuntary detrusor contraction.

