7.6.2 Multiplicity Adjustment

For the primary endpoint, due to multiple pairwise comparisons of each Dysport dose group versus placebo, a Hochberg correction will be applied to control the type one error at 5% significance level. The p-values from the two pairwise tests are ordered in magnitude from largest to smallest.

If both p-values for the two primary tests (the test of 600 U vs. placebo and the test of 800 U vs. placebo) are lower than 0.05, both will be declared statistically significant. If one of the primary tests has a p-value greater or equal to 0.05, then the other test will be declared statistically significant if its p-value is lower than 0.025 (and thus half of the overall experiment wise alpha of 0.05).

The six ordered secondary endpoints will be tested for both doses at the 0.05 level (using a hierarchical methodology) if, for both doses, the two primary tests achieve a p-value lower than 0.05. If one of the primary tests has a p-value greater or equal to 0.05, and the other has a p-value lower than 0.025, secondary endpoints will be assessed (using hierarchical methodology) for the dose group with p-value lower than 0.025, at the 0.025 significance level.

In order to control the family-wise type one error, the following hierarchical testing procedure will be applied for the testing of the superiority of both Dysport doses to placebo for the primary and selected secondary endpoints (ordered as described in Section 7.6.5):

- Step 1: The Dysport 600 U and Dysport 800 U will be compared to placebo on the primary endpoint. If the p-values associated with both doses are <0.05 then both doses will be declared statistically significant and the testing will proceed at the 0.05 level from step 2 onwards. If one dose has $p \geq 0.05$ but the other has $p < 0.025$ (significant dose) then testing will proceed at the 0.025 level from step 2 onwards on the significant dose only. If both dose groups have $p \geq 0.05$ or one dose group has $p \geq 0.05$ and the other dose group has $p \geq 0.025$, the testing procedure will be stopped.
- Step 2: The Dysport 600 U and Dysport 800 U will be compared to placebo for the first hierarchical secondary endpoint. Testing will be at the significance level defined in step 1 (0.05 or 0.025). If the p-value associated with this test is lower than the significance level defined in step 1 then it will be considered significant and testing will proceed to step 3. Otherwise the testing procedure will be stopped.

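### The logistic model for no IDCs at Week 6 (hierarchical endpoint 5) carries no baseline covariate; adding screening MCC may gain some power, by an amount the documents do not determine

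*SAP*

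**What the plan says.** SAP 7.6.5 sets out six ordered secondary endpoints at Week 6 and a model for each.

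- **Endpoints 1 to 3** (MCC, maximum detrusor pressure (MDP), volume at first IDC): ANCOVA. "The model will be the same as the sensitivity analyses for the primary efficacy endpoint in 7.6.4.2". That section lists treatment, the strata "and study baseline value of weekly number of UI episodes as covariates".
- **Endpoint 4** (no UI episodes, binary): logistic GLMM with a baseline term. "The study baseline value will be weekly number of UI episodes".
- **Endpoint 5** (no IDCs, binary): logistic regression. "The model will include treatment group, and stratification variables". The readable text has no baseline term.
- **Endpoint 6** (I-QoL total score): MMRM. "The model will be the same as primary analysis model in section 7.6.3". The model in SAP 7.6.3 includes a baseline value.

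SAP 7.6.6.2 mentions a logistic regression for no IDC again and lists no covariates.

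On the data available, Protocol 7.3.2 states: "All subjects will have a standardised urodynamic (filling cystometry) assessment at Screening and again at Week 6". Central readers determine the values that are analysed. Entry is handled differently: "During Screening the site will determine if the subject has NDO via the presence of IDCs (inclusion criterion #15"), and the central reader does not confirm that finding.

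On the error rate, SAP 7.6.2 states: "The six ordered secondary endpoints will be tested for both doses at the 0.05 level" if both primary tests succeed. The level is 0.025 if only one dose succeeds. Testing moves to the next endpoint only after significance on the one before.

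**The concern.** Endpoint 5 is the only hierarchical model without a baseline value. Its binary scale does not explain this, because endpoint 4 is also binary and has one. In a logistic model, adjusting for a prognostic baseline variable raises the power of the treatment test. It also protects against chance imbalance in that variable. The trial already schedules candidate variables for every subject at no extra burden.

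What is at stake is the chance of passing endpoint 5 and, through the fixed sequence, of reaching a formal test of endpoint 6, I-QoL.

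**Working it through.** **The plan's own figure.** The documents give no power and no assumed rates for endpoint 5. The only sample size calculation is for the primary endpoint (difference 21 − 12 = 9, SD 20, two-sided alpha 0.025, power 80%). The normal approximation is n = 2 × (20/9)² × (z₀.₉₈₇₅ + z₀.₈₀)², which gives 94 per arm. The two-sample noncentral t calculation gives 96 per arm (power 80.4%), matching the stated 96.

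**Inputs for endpoint 5.**
- From the documents: 110 subjects per arm with the placebo sequences pooled; 10% dropout to Week 6, so 110 × 0.90 = 99 evaluable per arm; two-sided alpha 0.05; two binary strata.
- Assumed: the no-IDC rates, the covariate's odds ratio per SD, a normally distributed covariate, complete covariate data and 50/50 strata.

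**Method.** Outcomes follow logit P(no IDC) = a_arm + γx, where x is a standard normal baseline value, γ is the log odds ratio per SD, and each a_arm is set to give the assumed rate in that arm. Each simulated trial is analysed twice by likelihood-ratio test of treatment: with treatment and strata only, as planned, and with x added.

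**Results** (power per dose, 1,500 trials per scenario, simulation error about 1 to 2 points):

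| Odds ratio of x per SD | 15% vs 30%: planned → with x | 20% vs 36%: planned → with x |
|---|---|---|
| 1.0 (not prognostic) | 75% → 75% | 70% → 70% |
| 1.65 | 74% → 76% | 70% → 73% |
| 2.2 | 73% → 78% | 71% → 75% |
| 3.0 | 74% → 80% | 71% → 78% |

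Allowing for simulation error, repeat runs put the gain at about 0 points at 1.0, about 2 at 1.65, 3 to 5 at 2.2 and 6 to 9 at 3.0.

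**Other rates.** With a Wald test and assumed rates of 5% vs 17%, 10% vs 25% and 20% vs 38% (4,000 trials each), the pattern is the same:

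| Odds ratio per SD | Gain at alpha 0.05 (points) | Gain at alpha 0.025 (points) |
|---|---|---|
| 1.0 | about 0 | about 0 |
| 1.65 | +1 to +3 | +1 to +3 |
| 2.7 | +3 to +6 | +4 to +7 |
| 4.5 | +8 to +10 | +10 to +13 |

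**Missing baseline values.** The documents give no rate of unusable baseline traces, so 10% missing at random was assumed. If those subjects are dropped, power falls about 3 to 4 points below the planned model at odds ratios of 1.0 to 1.65, and no gain is left at 2.2. If the missing value is replaced by the pooled mean across arms, the loss at 1.0 is no more than 0.4 points and the gains at the higher odds ratios are kept.

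**Which variable.** Presence of an IDC at Screening cannot serve, because it is an entry condition and so nearly constant. Volume at first IDC needs an IDC on the trace. Since the central reader does not confirm the screening IDC, the central value may be undefined for some subjects. The imputation from MCC in SAP 6.2.1.1 covers only a missing post-treatment IDC. MCC needs no IDC: under Table 20 of the Protocol it can be the total instilled volume.

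**The case against.** The best case for the plan is that each model adjusts for the baseline of its own measure, and that this endpoint has no useful baseline of its own. On that view the omission is deliberate and not an inconsistency. This largely stands. It explains the choice, but it does not show that a related continuous value would be of no use.

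A reader might infer that endpoint 5 departs from a pattern of urodynamic adjustment. The readable text does not support this: endpoint 4 names weekly UI episodes, endpoint 6 is a questionnaire score, and endpoints 1 to 3, read literally through SAP 7.6.4.2, also carry weekly UI episodes.

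A reader might also infer a definite loss of power. No passage says how well baseline MCC predicts absence of IDCs, and the loss is nil if it does not predict it at all.

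A third objection is that the covariate has a cost, because subjects without a usable baseline would drop out of the model. That is correct under complete-case analysis and could outweigh a modest gain. It is met by a missing-value rule, not by leaving the covariate out.

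Two further limits stand. Endpoint 5 is reached only after the primary and four secondary endpoints succeed, and it affects only endpoint 6. One covariate adjusts for one measure and would not remove all chance imbalance in bladder severity.

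**Conclusion.** The point holds as an optional efficiency improvement. The planned test is valid under randomisation: nothing here suggests bias or an inflated type I error, and the plan contains no contradiction on this point.

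The size depends almost wholly on an unknown, the prognostic strength of baseline MCC. Under the main assumptions (99 per arm, alpha 0.05, 15% vs 30% or 20% vs 36%) it runs from about 0 to 9 points of power per dose for odds ratios from 1.0 to 3.0 per SD, and it is about 2 points for a modest predictor.

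The SAS code for this model is redacted, so the conclusion rests on the readable text alone.

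**What to change.** Before unblinding, amend SAP 7.6.5 so that the endpoint 5 model reads: treatment group, aetiology of NDO, prior intradetrusor BTX-A use, and centrally read baseline MCC as a continuous covariate. Add that a missing baseline MCC is replaced by the pooled mean across arms, so that no subject is dropped. The value comes from a trace recorded before randomisation and the mean ignores treatment arm, so the rule does not favour either arm. Apply the same model to the no-IDC logistic regression in SAP 7.6.6.2, and check that the program code agrees.

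The cost is a clause in each of two sections and no new data. The odds ratio becomes conditional on one more covariate, as it already is on the strata.
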